### Exploring biomarkers in the heat and moisture exchange filters

## 2. Purpose, rationale, hypothesis and background

---

**Purpose:** To investigate if standard heat and moisture exchange (HME) filters contain endogenous proteins, that can be used for diagnostic purposes in patients undergoing elective major non-malignant surgery. Pulmonary complications are common in these patients and this pilot-study will investigate if human proteins are contained in the HME filters.

**Rationale for the project:** Patients undergoing major surgery are invasively mechanical ventilated during anaesthesia. In the ventilatory circle, a HME filter is inserted near the tracheal tube to warm and humidify the inhaled air to prevent drying of the airway mucosa. The HME filter also traps the exhaled heat and moist from the patient's lungs and releases the stored heat and moisture. The HME filters contains an electrostatic filter, which might catch exhaled human proteins without releasing them during ventilation. Previous studies have explored the potential for diagnosing medical conditions based on exhaled proteins collected by special devices, and together they prove the principle of exhaled breath diagnostics.

The HME filters are routinely discarded when the patients are extubated, but maybe they contain a goldmine of information about the patients. This project investigates if exhaled breath proteins can be collected using standard HME filters.

**Project hypothesis:** The HME filters from surgical patients on mechanical ventilation contains endogenous proteins and extracellular vesicles and can be a non-invasive source for diagnostics and monitoring.

**Project objective and aims:** The project will investigate the exhaled proteins and extracellular vesicles from HME filters from patients undergoing elective surgery after invasive mechanical ventilation during anaesthesia.

#### *Primary aim:*

- Measure total amount of human protein in HME filters and compare to total protein in blood.

#### *Secondary aims:*

- Assess variation in exhaled breath protein concentration.
- Measure HME filter protein contents according to length of invasive mechanical ventilation.
- Investigate if protein molecular weight and isoelectric point has influence on representation in HME filters.
- Investigate if extracellular vesicles from the exhaled breath can be captured and analyzed from HME filters.
- Investigate if the HME filter protein content differs between intravenous versus inhalation anaesthesia.

**Background:** Postoperative pulmonary complications (PPCs) are common and associated with increased morbidity and mortality. The diagnoses varies from atelectasis, pneumonia, acute lung injury, pneumothorax, and pulmonary embolism among others. Several perioperative therapies have been evaluated to decrease the risk of PPCs, but the evidence is still sparse. The major challenge is to identify patients at risk as there is no specific biomarker for acute lung tissue injury. The clinic-pathological understanding of PPCs., and hence precise diagnosis and effective prevention and treatment are challenged because it is hard to get representative samples from the lungs of patients with acute respiratory failure without use of invasive methods such as bronchoalveolar lavages (BAL) or biopsies. However, these methods itself increases the risk of PPCs. During a BAL, the surfactant of the lungs is washed out, which increases the risk of alveolar collapse and lung biopsies increase the risk of pneumothorax, which highlights the unmet need for techniques for non-invasive biospecimen sampling from the airways. This was recently addressed in a new working group report from the American Thoracic Society, with emphasis on HME filter fluid, non-bronchoscopic BAL, endotracheal aspirates and sputum samples.

One of the authors of the working group report have specifically investigated the proteins in the fluid, that can be retained from some HME filter types. Our group has demonstrated diagnostic potential of exhaled breath proteins and efficient exhaled breath protein-capture by electrostatic filter, which is the matrix in HME filters (manus in preparation). We therefore envision, that analysis of the proteins in the filter matrix, not restricted to the HME filter fluid, will identify significantly more protein and thus serve as an efficient new non-invasive source for biomarkers.

A recent study has detected lung tissue derived extracellular vesicles in exhaled breath condensate. Extracellular vesicles (EVs) are nano-sized, membrane-bound particles secreted by all cell types, ranging from 30-5000 nanometers in diameter. These lipid bilayer-enclosed structures carry diverse molecular cargo including proteins, RNA, and DNA that directly reflects the physiological state of their parent cells.

### **3. Methods, Statistics and Study Subjects**

---

#### **Study subjects and design:**

This study is a prospective clinical study addressing the objectives and aims. We will include adult patients who are scheduled for elective surgery for non-malignant conditions under general anesthesia with invasive mechanical ventilation. The written and oral study information will be provided at the standard preoperative consultation with the anesthesiologist the day before elective surgery. We will include 10 patients, in- and exclusion criteria are elaborated in section 5.

#### **Protein measurements and detection of extracellular vesicles:**

HME filters: Total protein concentration will be estimated by elution of the proteins from the dismantled HME filters using SDS buffer solutions and fluorescence analysis. Single proteins, as indicated in table 1, will be measured by standard biochemical analysis at the Department of

Clinical Biochemistry. Besides, we will use flowcytometry to check potential presence of extracellular vesicles using CD9 as specific marker of this.

Blood samples: Standard clinical biochemical analysis for the proteins in table 1.

Table 1. List of proteins to measure in HME filters ( mg/10 Liter exhaled air) and blood.			
Protein	MW (kDa)	Isoelectric Point (pI)	Plasma Concentration (g/L)
IgM	~900	5.0	0.5–2
Fibrinogen	340	5.5	2–4
IgA (dimer)	160–400	6.0	1–4
Complement C3	190	5.5	0.8–1.8
Haptoglobin	45–100	6.0	0.3–2
$\alpha$ 1-antitrypsin	52	5.5	0.9–2
Ceruloplasmin	132	5.5	0.2–0.6
IgG	150	7.0	7–16
Transferrin	80	6.5	2–3
Albumin	66	4.7	35–50
Apolipoprotein A-I	28	5.2	1–1.5
Apolipoprotein B-100	550	6.0	0.9–1.2
IgD	180	7.0	<0.05
IgE	190	7.0	<0.05
Complement Factor H	155	5.0	0.2–0.4
$\beta$ 2-microglobulin	12	11	0.002–0.003
Cytokines (IL-6, TNF- $\alpha$ )	21–25	6–7	<0.001
$\alpha$ 2-macroglobulin	720	5.3	1–3
Plasminogen	92	6.0	0.2–0.4
Fibrinogen Fragments	50–250	5–6	variable

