## **7. Biological data**

[figure not shown]
---

We will collect the HME filter and ask for two arterial blood samples (4 mL EDTA blood + 3.5 mL citrate blood) from each study participant. See Figure 1 for overview of samples. The HME filter is inserted in the respiratory circuit as part of the standard procedure in patients being invasively mechanically ventilated. At the time of extubation, we will collect the blood samples and the HME filter and store them in the projects research biobank until analysis, as all samples must be analyzed simultaneously. Blood samples will be double centrifuged to obtain platelet poor plasma supernatants (whole blood: 2500 g for 15 minutes, supernatant: 2500 g for 15 minutes) before transfer to the project's research biobank.

The complete amount of exhaled breath proteins captured in the HME filters will be used in analysis, no material will be left after analysis. A minor amount of platelet poor plasma will probably be left after analysis. These remains will be destructed after all the planned protein analysis are finished.

The laboratory data (protein measurements) will be stored at the logged Q-drive at Department of Hematology, Aalborg University Hospital, North Denmark Region.

Data will be deleted after project end, which is defined in the Article 30 registration as 31. December 2031.

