## **9. Handling of personal data**

---

In this study, the law of handling of personal data will be followed, cf. *Komitéloven §20, stk. 1, nr. 4 and 6*. The project will include collection of personal data and analyses performed on the exhaled breath referable to the patients and control subjects included. The project is following the General Data Protection Regulation and the project has been registered at North Denmark Region's record of processing activities (F2025-193). Published data will be anonymized.

10: There are no external partners in this project.

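### The primary total-protein result cannot be attributed to exhaled human protein: the stated assay is not described as human-specific and no unused filter is listed for processing

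*Protocol*

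**What the plan says.** Protocol section 2 poses a presence question: "this pilot-study will investigate if human proteins are contained in the HME filters". The primary aim in the same section is a quantity: "Measure total amount of human protein in HME filters and compare to total protein in blood".

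Section 3, under protein measurements, gives one method for that quantity: "Total protein concentration will be estimated by elution of the proteins from the dismantled HME filters using SDS buffer solutions and fluorescence analysis". Two further filter read-outs follow. "Single proteins, as indicated in table 1, will be measured by standard biochemical analysis at the Department of" Clinical Biochemistry, and for vesicles "we will use flowcytometry to check potential presence of extracellular vesicles using CD9 as specific marker of this". The title of Table 1 gives the unit for the listed proteins in the filters as mg per 10 litres of exhaled air.

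Section 7 lists the material: "We will collect the HME filter and ask for two arterial blood samples (4 mL EDTA blood + 3.5 mL citrate blood) from each study participant". It adds that all samples are to be analysed together and that the protein captured in the filters will be used up. Section 4 plans plots, t-tests, correlation coefficients and coefficients of variation.

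**The concern.** The primary aim names human protein, but SDS elution with a fluorescence read-out, as described, gives a general protein signal. Nothing in the text separates protein exhaled by the patient from manufacturing residue, material picked up in handling, or signal from the buffer and the filter matrix. The usual way to learn the size of that background is to take unused filters through the same steps. None is listed.

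Three things are at stake:

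- **The primary estimate.** It is exhaled protein plus an unknown background, and cannot be read as human protein alone.
- **The secondary aims on ventilation length and on variation.** A background that is constant per filter, divided by exhaled volume, weighs most on short operations.
- **Later repair.** The captured protein is consumed in one joint run, so the used filters cannot be re-run beside blanks afterwards. An analysis plan cannot subtract a background that nobody measured. This is a matter of which specimens are processed, not of analysis detail.

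**Working it through.** **Step 1. Does each stated measurement deliver the primary quantity?**

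| Filter read-out (section 3) | Bears on human protein being present? | Gives total human protein? | Filter blank stated? |
|---|---|---|---|
| SDS elution with fluorescence | Not by itself; no human-specific step described | Gives a total, but not a human one | No |
| Table 1 single proteins | Yes | No; listed proteins only | No |
| CD9 by flow cytometry | Yes, for vesicles | No | No |

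No row gives the quantity in the primary aim, and no row has a stated filter blank. The text also does not say how the single-protein assays perform in an SDS eluate.

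**Step 2. How much could a constant background distort values per 10 L?**

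The protocol gives no background level, so there is no figure of its own to reproduce. The following is an illustration.

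Inputs:
- b = background as a share of the signal from a one-hour filter; assumed 0.05, 0.10 and 0.30.
- r = exhaled volume relative to one hour; r = 1 for 1 h and r = 5 for 5 h, assuming constant minute ventilation. Section 5 requires expected ventilation of more than 1 hour, so 1 h is the lower end of what is planned. The 5 h end is assumed.
- True captured protein is assumed proportional to exhaled volume, so it equals (1 − b) × r.
- The background is assumed the same for every filter.

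Overstatement factor of the value per 10 L:

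(b + (1 − b) × r) / ((1 − b) × r)

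| b | Factor at 1 h | Factor at 5 h | Ratio 5 h / 1 h | False decline |
|---|---|---|---|---|
| 0.05 | 1.00/0.95 = 1.053 | 4.80/4.75 = 1.011 | 0.96 | 4% |
| 0.10 | 1.00/0.90 = 1.111 | 4.60/4.50 = 1.022 | 0.92 | 8% |
| 0.30 | 1.00/0.70 = 1.429 | 3.80/3.50 = 1.086 | 0.76 | 24% |

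The ratio simplifies to 1 − b × (1 − 1/r). At r = 5 the false decline is therefore 0.8 × b. The true value per 10 L is constant in this illustration, so the whole decline comes from background.

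**Step 3. Does the scaling apply to total protein?** The unit per 10 L stands only in the Table 1 title, for the single proteins. Section 8 records total exhaled litres per filter, so total protein could be scaled the same way, but the protocol does not say that it will be. Step 2 is therefore conditional on that scaling.

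**The case against.** A reader might infer that the study's basic question cannot be answered at all. Section 3 does not support that. The named plasma proteins are also to be measured in the filters, and CD9 is checked; both bear directly on whether human protein is there. This stands, and it limits the point to the primary total.

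A reader might also infer that any signal will be declared exhaled human protein, so that the study cannot fail. The protocol has no detection rule and no test against zero. A simulation with zero human protein and background only (all inputs assumed) shows that a test of 10 filters against zero would find protein in 97–100% of runs, against about 2–6% when compared with 3 to 10 blanks. Since section 4 proposes no such test, those rates illustrate why blanks help and do not describe the planned analysis.

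Next, an unlisted blank is not proof that none will be run. The figure in section 7 is not shown (its title refers to samples per patient), laboratory procedures are not at hand, and section 4 says the collaborating laboratory tests analytical validity routinely. So the fair wording is that no blank is stated. For a specimen that decides what the primary result means, that is still a gap in the protocol.

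It would also be too strong to say the design has no control of any kind, since each patient's blood is a matched comparator. Blood does not measure filter background, however. Nor does section 9's reference to "analyses performed on the exhaled breath referable to the patients and control subjects included" help: those controls are defined nowhere, and they are people, not filters.

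Finally, the background share is assumed, and at 5% the distortion is small. That is correct, and it is why a range is shown. The documents do not say where in that range, or outside it, the real value lies.

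**Conclusion.** The concern holds for the primary total-protein result. As written, that result cannot be attributed to exhaled human protein as opposed to filter, buffer or handling background. The single-protein and CD9 read-outs can support presence, but they do not supply the total and carry no stated filter blank of their own.

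The bias in the total itself cannot be sized from the documents. For values per 10 L, the false decline from 1 h to 5 h is about 4%, 8% or 24% for an assumed background of 5%, 10% or 30% of the one-hour signal. This rests on a constant background per filter, constant minute ventilation, true protein proportional to exhaled volume, and scaling by volume. The attribution problem rests on none of these assumptions.

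The matter should be settled before the single joint assay run, because the captured material is consumed in it.

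**What to change.** In sections 3 and 7 of the protocol:

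1. Add several unused filters of the same model and lot, for example 5. Handle, store, dismantle and elute them exactly as the used ones, in the same simultaneous run.
2. Report the primary outcome as blank-corrected total protein.
3. Define detected, for total protein and for each single protein, relative to the blanks, for example above the blank mean + 3 SD. The number of blanks and the multiple are examples for the laboratory to settle; the documents do not determine them.
4. State that the word human rests on the single-protein assays. Blank correction removes background but does not make the fluorescence total human-specific.

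The cost is a few extra filters and assay wells, with no added patients or procedures, and somewhat lower reported amounts.

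Spiking further unused filters to measure elution recovery is optional. It would help the secondary aim on molecular weight and isoelectric point, because the eluate mixes capture with recovery. If leftover plasma were used, section 7 would have to change: it expects only a small remainder and has it destroyed once the planned analyses are done.

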#### 4. Sample size and statistics

We cannot perform a regular power calculation before we have the results from this study, which will form the basis for new studies of exhaled breath proteomics based on collection from HME filters. Based on experience from the project collaborators at Department of Clinical Biochemistry, who as a daily task perform test of biochemical analysis validity and variation, 10 study subjects is a suitable sample size to investigate the project aims.

Spaghetti -and box plots will be used to depict the protein concentrations, microdata from spaghetti plots will not be published. To compare means and inter-individual, we will apply the t-test if underlying assumptions are met, and report interclass correlation coefficients as well as coefficients of variation. The statistical analyses will be supervised by biostatistician from the department of hematology.

#### 5. Inclusion and Exclusion criteria

### **Inclusion criteria**

- ≥18 years, able to understand study information in Danish.
- Admitted for elective surgery for non-malignant conditions with either intravenous or inhalation anaesthesia and invasive mechanical ventilation according to standard practice.
- Expected invasive mechanical ventilation > 1 hour.
- Possess legal capacity.
- Informed, signed consent is obtained.

### **Exclusion criteria**

- Patients who are transferred to the ICU for continuous invasive mechanical ventilation after end of elective surgery.
- Known chronic lung disease.

## **6. Risks and adverse events**

---

Since this project uses HME filters, that are normally discarded, we don't expect that the patients will experience discomfort because of collection of the exhaled breath proteins in this project.

Arterial blood sample will be collected from the arterial line placed during anaesthesia according to standard practice. The volume of blood (4 mL EDTA blood + 3,5 mL citrate blood) is minimal and does not give rise to any risk for the participants.

## **7. Biological data**

[figure not shown]
---

We will collect the HME filter and ask for two arterial blood samples (4 mL EDTA blood + 3.5 mL citrate blood) from each study participant. See Figure 1 for overview of samples. The HME filter is inserted in the respiratory circuit as part of the standard procedure in patients being invasively mechanically ventilated. At the time of extubation, we will collect the blood samples and the HME filter and store them in the projects research biobank until analysis, as all samples must be analyzed simultaneously. Blood samples will be double centrifuged to obtain platelet poor plasma supernatants (whole blood: 2500 g for 15 minutes, supernatant: 2500 g for 15 minutes) before transfer to the project's research biobank.

The complete amount of exhaled breath proteins captured in the HME filters will be used in analysis, no material will be left after analysis. A minor amount of platelet poor plasma will probably be left after analysis. These remains will be destructed after all the planned protein analysis are finished.

The laboratory data (protein measurements) will be stored at the logged Q-drive at Department of Hematology, Aalborg University Hospital, North Denmark Region.

Data will be deleted after project end, which is defined in the Article 30 registration as 31. December 2031.

**Figure 1. Overview of biological samples per patient.**

## 8. Data from electronic medical records

Patients who are scheduled for elective major surgery will be identified at the weekly list of surgical patients, which is preplanned Thursday or Friday the week before surgery. Based on the type of surgery and thereby the type of anaesthesia, the anaesthetists who is member of the project team, will identify patients who fulfill the inclusion criteria. The data below will be transferred from the surgical lists to the project anaesthetists to identify potential project participants. We expect that these informations will be transferred to researchers from a maximum of 25 potential project participants as we expect that most invited patients will participate in the study:

- CPR number, name and age.
- Type of elective surgery.
- Length of invasive mechanical ventilation (minutes).

The following data will be transferred after informed consent from included project participants. Data are obtained directly from the patients at the conversation with the project worker, obtained directly from the mechanical ventilator during surgery or electronic medical records:

- Date of elective surgery.
- Total liters of exhaled air per HME filter during invasive mechanical ventilation.
- Ventilatory parameters: Tidal volume (ml/kg), respiratory frequency/minute, peak pressure (cmH2O), positive end-expiratory pressure (cmH2O), end-tidal CO2 (kPa).
- Length of invasive mechanical ventilation.
- pH, pO2 and pCO2 from arterial blood gas analysis, if analyzed during surgery.

The clinical data will be entered into the projects REDcap database at Aalborg University Hospital.

An informed consent gives the investigator and her delegates direct access to obtain relevant information from medical records, including electronic medical records, to see information regarding the study participants' health conditions, which is necessary for the projects' execution – hereunder quality control and monitoring, cf. *Komitéloven §3, stk. 3*.

## **9. Handling of personal data**

---

In this study, the law of handling of personal data will be followed, cf. *Komitéloven §20, stk. 1, nr. 4 and 6*. The project will include collection of personal data and analyses performed on the exhaled breath referable to the patients and control subjects included. The project is following the General Data Protection Regulation and the project has been registered at North Denmark Region's record of processing activities (F2025-193). Published data will be anonymized.

10: There are no external partners in this project.

## **11. Economy**

---

[name] is the project principal investigator. She has taken initiative to this study, which is designed and conducted in a collaboration between the Department of Hematology, the Department of Anesthesia and Intensive Care and the Department of Clinical Biochemistry at Aalborg University Hospital. The project will be financed by internal funds at the involved departments. Two medical students will contribute to the participant recruitment and laboratory work as part of their master thesis. Blood collection tubes and expenses to laboratory analysis are covered by the Department of Clinical Biochemistry. Companies are not involved in the project. [name]'s salary for research time is covered by a career grant for clinical research from the Novo Nordisk Foundation (Grant ID: NNF24OC0089034), but the project expenses are not covered by this grant.

